**B. Identify all procedures, interventions, evaluations and tests that are performed solely for research purposes.**

Functional analyses and FCT are common clinical components in the assessment and treatment of problem behavior. These components would be implemented regardless of participation in this research study.

Although caregiver pretests and posttests are common components of clinical cases, we will not bill for these procedures. For behavioral interventions, we obtain authorizations from insurance companies that cover a span of time (e.g., a month, two months, four months) rather than authorization for specific tests (e.g., the pretest). To gain additional time with a client, we then have to request a reauthorization that often varies in time from the initial authorization. Thus, for the waitlist-control group, this would mean that obtaining authorization to conduct the pretest would use up one of the client's authorization periods

during the wait period despite the client not receiving services during this time, and reauthorization to bill for the posttest several months later. Therefore, we will consider all of the pretests and posttests as procedures for research and only bill for the clinical services received during the treatment portion of the admission.

**C. Identify all procedures, interventions, evaluations and tests that are performed more frequently than they would be if the subject was not participating in the research.**

The pretests and posttests are being conducted for research purposes and the additional pretest for the wait-list control group is occurring more frequently (i.e., twice) than what would occur typically in a clinical admission.

**D. Describe briefly the statistical methods used to analyze the data.**

Within-participant data analysis

We will use both structured visual inspection and appropriate statistical methods to analyze each participants single-case data sets. The visual-inspection procedures developed and validated by members of our team are highly reliable (IOA  $\geq .95$ ). In addition, we will use the Allison and Gorman (1993) regression procedure to calculate significance levels and effect sizes for single-case designs. Completing these analyses with individual children will allow us to determine, with a high degree of certainty, how many children responded in the predicted pattern.

Group statistics

To compare the changes from pretest to posttest, we will conduct analyses of group differences (FCT treatment vs. wait list) on the primary dependent variables using an analysis of covariance with the parent baseline pretest as the covariate and the parent baseline posttest the dependent variable.

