The goal of this study is to compare FCT (which is used clinically with the majority of our patients and is considered best practice for treating destructive behavior that occurs for social reasons [e.g., to access attention, preferred toys, or to escape from unpleasant activities]) to a waitlist control group across a large number of children with destructive behavior to evaluate the generality of FCT effectiveness. We will evaluate rates of destructive behavior with each patient during a pretest baseline and again following FCT (approximately four months later) and/or the waitlist control duration (again, approximately four months later). All children assigned to the waitlist-control condition will be offered FCT services by our clinic at the end of the four-month waitlist period. These children will again be tested following four months of FCT (i.e., posttest). Therefore, children assigned to the FCT condition will be tested twice (one pretest and one posttest), and children assigned to the waitlist-control condition will be tested thrice (one pretest, a second pretest following a four-month waitlist period, and one posttest).

We will pair participants to dyads and randomly assign one participant to the FCT condition and one participant to the waitlist control condition. The exact duration of the waitlist condition for one participant will be matched to the duration of the FCT participants admission. Historically, most children complete FCT within four months.

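### Section II.11.D makes the posttest the ANCOVA outcome, but the plan's labels put the wait-list posttest after those children have had FCT, while its design text points to the end of the wait

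*Combined protocol and SAP*

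**What the plan says.** Section II.11.D, under Group statistics, describes its model as "an analysis of covariance with the parent baseline pretest as the covariate and the parent baseline posttest the dependent variable". No wait-list visit is named for that outcome. The purpose given for the model, in the same sentence of the plan, is "analyses of group differences (FCT treatment vs. wait list) on the primary dependent variables".

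The plan's use of the word posttest is set elsewhere:

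- **Protocol Abstract (Section II.1), labels.** After the wait, the control children are offered FCT. "These children will again be tested following four months of FCT (i.e., posttest"). Their three tests are then listed as a pretest, "a second pretest following a four-month waitlist period, and one posttest".
- **Section II.11.C.** The extra wait-list test is again counted as a pretest: "the additional pretest for the wait-list control group is occurring more frequently (i.e., twice").
- **Section II.11.B.** In a discussion of billing for the wait-list group there is a reference to "reauthorization to bill for the posttest several months later". It does not say whether FCT comes before that test.
- **Section II.11.A.** A Parent Baseline Pretest is described and placed before assignment. No posttest is described.

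Other text bears on when the arms are to be compared:

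- **Protocol Abstract, design.** Rates are measured at a pretest and "again following FCT (approximately four months later) and/or the waitlist control duration (again, approximately four months later"). On pairing, it says: "The exact duration of the waitlist condition for one participant will be matched to the duration of the FCT participants admission".
- **Section II.3.** The stated goal is a comparison of FCT with a wait-list control group.

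**The concern.** The analysis section uses a term that the plan defines elsewhere, and for one arm that definition gives the wrong visit. An analyst who looks up the wait-list posttest in the Protocol Abstract finds a test taken after the control children have crossed over to FCT. At that point there is no untreated group left, and the two arms are measured at different times after the pretest.

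The background section justifies the trial by the absence of randomized evidence for FCT, and this ANCOVA is the only analysis that uses the randomization. Read by label, it loses that contrast.

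The likelier course is that the analyst sees what was meant and uses the end-of-wait test. Even then, the primary outcome visit would have been chosen against the plan's own labels, with no written rule made before the data were seen. Section 15.E has the investigator graphing every participant's data daily, so such a choice would not be blind to results. Section 4.A also sets further enrolment by a power analysis after eight children and does not say which outcome it uses. If it uses the ANCOVA outcome, the ambiguity reaches the sample size too.

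**Working it through.** The plan states no effect size, SD or power for this analysis, so there is no figure of its own to reproduce. The check sets the two readings side by side, then works out the timing and the expected difference under each.

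**1. The two readings**

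| | Outcome, FCT child | Outcome, wait-list child | Wait-list child treated by then? |
|---|---|---|---|
| By label (Protocol Abstract, 11.C) | posttest | posttest | yes |
| By design text (Protocol Abstract, Section 3, contrast named in 11.D) | posttest | second pretest, end of wait | no |

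The covariate is not in doubt: 11.A places the Parent Baseline Pretest before assignment for every child.

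**2. Timing after the pretest**

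Let A be the FCT child's admission and B the wait-list child's own later admission. The wait is matched to A.

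- End-of-wait reading: A in both arms.
- Label reading: A for the FCT child, A + B for the wait-list child, so the gap is B.
- With A = B = about 4 months (Protocol Abstract): 4 versus 4 + 4 = 8 months.
- With A and B of 8 to 12 weeks, if the visit period in 11.A applies: 8 to 12 versus 16 to 24 weeks.

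**3. Expected difference (FCT arm minus wait-list arm, in points of the baseline rate)**

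Let R1 be the percentage reduction in the immediate arm, R2 the reduction in the delayed arm after its own FCT, and u the fall without treatment.

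- End of wait: (100 - R1) - (100 - u) = u - R1
- After FCT in both arms: (100 - R1) - (100 - R2) = R2 - R1

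Inputs: R1 = 90 is the Protocol Abstract's summary of earlier studies, not a stated expectation for parent-run tests. R1 = 70 and 50, u = 0 to 30, and R2 within 10 points of R1 are assumptions.

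| R1 | End of wait, u = 0 to u = 30 | Post-FCT, R2 = R1 - 10 to R1 + 10 | Largest post-FCT difference as share of smallest intended contrast |
|---|---|---|---|
| 90 | -90 to -60 | -10 to +10 | 10/60 = 17% |
| 70 | -70 to -40 | -10 to +10 | 10/40 = 25% |
| 50 | -50 to -20 | -10 to +10 | 10/20 = 50% |

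If R1 = R2, the post-FCT difference is 0 whatever the size of the effect. No SD, correlation or sample size enters this step.

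**4. What that does to the test (illustration only)**

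Take the plan's expected ceiling of 15 per arm. Assume a two-sided 5% level, R1 = 90, u = 0 and a residual SD of 0.5 to 2.0 times the baseline mean. With one covariate, df = 2 x 15 - 3 = 27, and the noncentrality is 0.9 / (SD x sqrt(2/15)).

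| Residual SD / baseline mean | Power, end-of-wait outcome | Rejection rate, post-FCT outcome with R1 = R2 |
|---|---|---|
| 0.5 | 99.7% | 5% |
| 1.0 | 66.1% | 5% |
| 1.5 | 35.4% | 5% |
| 2.0 | 22.1% | 5% |

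Under the label reading with equal effects, the test rejects only at its nominal error rate, however well FCT works.

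**The case against.** The strongest reply is that nobody would run the label reading. The sentence that uses the word posttest also names the contrast as FCT against wait list, and a child who has completed FCT is no longer on the wait list. The matched wait, the re-test at about four months in each arm and the stated goal all point the same way. The word may also be used loosely: the billing remark in 11.B can be read as calling the end-of-wait test a posttest. The form asks only for a brief description of methods. Finally, the post-FCT range restates the 10-point limit that was assumed, so the magnitudes describe a reading that is conceded to be the less likely one.

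Much of this stands. The intended visit is very probably the end of the wait, an analyst has little reason to prefer an outcome expected to show almost nothing, and the figures illustrate the consequence rather than predict a loss. These points bear on how serious the matter is.

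They do not remove it. The 11.B remark does not say whether FCT comes first, and 11.C then counts two wait-list pretests. No text links the second pretest to the ANCOVA outcome. Brevity explains a missing detail, but here the stated term, read with the plan's own definition, gives the wrong visit.

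**Conclusion.** The concern holds: the outcome in 11.D is wrong as written for the wait-list arm. Taken with the plan's own labels, it replaces the randomized contrast with a comparison of treated children at one versus two treatment-length intervals after the pretest. The expected difference is zero if FCT works equally in both arms, against 20 to 90 points of the baseline rate at the end of the wait over the assumed range of effects.

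The label conflict itself rests on no assumption, since it is in the text. The sizes rest on the assumed reductions, untreated change and 10-point limit, and the power figures also on the assumed SD and error level. Because the intent can be recovered from the design text, this should be fixed before analysis; it is not evidence that the wrong visit will be used.

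**What to change.** Add to Section II.11.D:

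> The dependent variable is the parent test at the end of the dyad's matched interval: for FCT children the posttest, and for wait-list children the second pretest, taken at the end of the wait. The covariate is the pre-assignment Parent Baseline Pretest for every child. The wait-list group's test after its own FCT is not an outcome in this between-group ANCOVA.

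The cost is two or three sentences. No visit or data collection is added, because the end-of-wait test is already scheduled.

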**CONFIDENTIALITY AND PRIVACY**

**12. Confidentiality and Privacy**

**A. Will research data be stored:**

**1) On a secure server at UNMC/TNMC/CH&MC/UNO?**

Yes

**2) On a local hard drive?**

No

**3) On a portable computer?**

Yes

**a) Is the portable computer encrypted and password protected?**

Yes

**4) On a flash drive?**

No

**5) In a database accessible through the internet?**

No

**6) In hard copy?**

No

**7) Other?**

No

**B. Will any of the following subject identifiers be recorded (at any time) in association with the research data?**

Yes

**1) Indicate the subject identifiers that will be recorded:**

- ◆ Name
- ◆ Postal address information: street address, city, county, precinct, ZIP code
- ◆ All elements of dates (except year) related to an individual (e.g. birth, admission, discharge)
- ◆ Telephone numbers
- Fax numbers
- ◆ Electronic mail addresses
- Social Security numbers
- ◆ Medical Record numbers
- ◆ Health plan beneficiary numbers
- Account numbers
- Certificate/license numbers
- Vehicle identifiers and serial numbers, including license plate numbers
- Device identifiers and serial numbers
- Web Universal Resource Locators (URLs)
- Internet Protocol (IP) address numbers
- Biometric identifiers, including finger and voice prints
- ◆ Full face photographic images [and any comparable images]

No identifiers will be maintained

**2) Will a unique subject identifying number, characteristic or code be used to protect the confidentiality of the data? This includes codes assigned by the investigator to link data to other identifiers like the subject's name or medical record number?**

Yes

**a) Where will the key, that links the unique subject identification code to the subject's name or other identifier, be stored?**

A master list with participant numbers and names will be kept separate from other data in a locked cabinet in the principal investigator's office.

**3) What is the justification for recording the specific identifiers listed above?**

Schedule appointments

Follow-up with subjects

♦ Other. Explain. Participants will be currently enrolled in the Severe Behavior Disorders Clinic in the Center for Autism Spectrum Disorders at the Munroe-Meyer Institute. The principal investigator will have access to the participant identifiers in order to follow up with subjects and schedule appointments.

**4) How long will the subject identifiers be maintained in association with the research data?**

Subject identifiers will be maintained for a minimum of seven years.

**5) How will the research data be archived or destroyed when the data is no longer required?**

Research data will be archived on an encrypted UNMC server. Video recordings for data collection purposes will be maintained up to a month following a given session before being deleted.

**6) Will research data that contain subject identifiers be disclosed to any other investigators at UNMC, TNMC, UNO or CH&MC who is not listed in Section I of this application?**

No

**7) Will research data that contain subject identifiers be disclosed to any investigators outside of UNMC, TNMC, UNO or CH&MC?**

No

**8) Will research data that contain subject identifiers be disclosed to any commercial sponsor or contract research organization (CRO)?**

No

**9) Will research data that contain subject identifiers be disclosed to any other external organization or entity?**

No

**C. What provisions will be in place to protect the subject's privacy? Check all that apply.**

- ◆ Obtaining consent in a private conference room or area
- ◆ Ensuring that only personnel listed on the IRB application Section I.3(A-E) are present during the consent process
- ◆ Ensuring that the fewest number of individuals possible are aware of the subject's participation in the research
- ◆ Ensuring that the research activities are performed in as private of a place as possible

Other. Explain.

**D. Does this research involve data banking at UNMC, TNMC, UNO or CH&MC for future research that is not related to this study?**

No

**E. Does this research involve data banking by an outside organization (e.g. NCI Cooperative Group, pharmaceutical company) for future, unspecified research that are not integral to the current research?**

No

## RISK/BENEFIT ASSESSMENT

### 13. Potential Risks

What are the potential risks associated with each research procedure, intervention, evaluation and/or test? If data is available, estimate the probability that a given harm may occur and its potential reversibility.

There is a potential for child and therapist injury as a result of the child's problem behavior. Problem behavior such as aggression, property destruction, or self-injury may be occasioned by presenting difficult demands, restricting access to preferred items, or activities or restricting access to caregiver attention. All therapists participating in the study have received formal training on how to appropriately and safely block problem behavior in a manner that minimizes these risks. If the child engages in problem behavior that may result in injury to the therapist, the therapist will have the option to wear protective equipment during the assessment (e.g., arm guards, chest and shoulder pads, etc.). If the

child's problem behavior appears to escalate to unsafe levels, the session will be ended and clinically-approved measures will be implemented to ensure the safety of the child. In the seven years we have served this population at MMI no children have sustained injuries that have required medical attention.

While completing questionnaires, such as the Parental Stress Index, some of the questions may make caregivers uncomfortable. We will inform caregivers that they are free to terminate the questionnaires or the study at any point and still receive services through our Severe Behavior Disorders clinic.

#### **14. Risk Classification**

**What is the overall risk classification of the research?**

Minimal risk

- ♦ Greater than minimal risk

#### **15. Minimization of Risk**

**A. Will the research utilize procedures that would already be performed on the subjects even if they chose not to participate in the research?**

Yes

**Describe the procedures.**

Functional analyses and FCT are best practice for identifying the function of socially maintained destructive behavior and developing treatment based upon the target function.

**B. Describe how the subjects of the research will be monitored by the investigators and other research personnel to ensure their safety.**

Participants will have the investigators contact information if any situation occurs in which they are concerned. Additionally, if something happens in the home and the child's destructive behavior escalates, the caregivers are instructed to proceed as they typically would in contacting the police for immediate help. Also, if anyone sustains concerning injuries outside of the clinic hours, the caregivers will be instructed to contact an urgent care or emergency care facility, and follow up with the investigators the following day.

Additionally, weekly meetings will be scheduled to address any caregiver concerns.

**C. Describe the process by which the PI will be informed and how the PI, in turn, will inform other research staff about events concerning subject safety (including (a) interim results; (b) unanticipated problems involving risks to subjects or others; (c) noncompliance; (d) complaints).**

**1) At UNMC/TNMC/CH&MC and/or UNO (check all that apply)**

Not applicable. The PI is the only person listed in Section I of the IRB Application.

- ◆ By email or campus mail (for events which do not constitute immediate subject safety hazards)
- ◆ By phone
- ◆ By in-person meeting

Other. Explain.

**2) At external study sites under the oversight of the Joint Pediatric IRB as applicable (check all that apply)**

By email or mail (for events which do not constitute immediate subject safety hazards)

By phone

By in-person meeting or teleconference

- ◆ Other. Explain. The current investigation will not occur at external sites.

**D. Describe the auditing plan for research conducted:**

**1) Within the Organization (UNMC, TNMC, UNO or CH&MC), identify who will conduct the audits and specify the audit frequency..**

All study personnel will conduct ongoing review of compliance with the protocol. Any violations of the protocol will be immediately reported to the Principal Investigator and the IRB. All study personnel will also conduct a comprehensive retrospective review of compliance with the protocol at the completion of each cohort (for a total of 5 comprehensive retrospective reviews of compliance with the protocol). Any violations of the protocol will be immediately reported to the Principal Investigator and the IRB.

**2) At external study sites under the oversight of the Joint Pediatric IRB, identify who will conduct the audits and specify the audit frequency.**

The current investigation will not occur at external sites.

**E. Describe the data monitoring plan.**

**1) Who will perform the ongoing data and safety analysis?**

The primary investigator and treatment team will meet on a daily basis to review the data and the safety of participants.

**2) What is the frequency of data analysis?**

The primary investigator will graph the data for all participants daily.

**F. Describe the specific criteria by which the investigator would withdraw individual subjects from the research.**

If the child exhibits severe problem behavior causing bodily damage to themselves or

others, the investigators will discuss continued participation in the study with the child's parents and teachers. If participants continuously miss appointments without reasonable excuses (e.g., 2 consecutive unexplained absences) the parents will be warned that their participation in the study may be terminated.

**G. Describe the specific criteria for halting or early termination of the study.**

When unexpected problems are encountered (e.g., unexpected risk to the participants are observed), the research project will be halted and the participants continued participation in the study will be discussed with his/her legal guardian(s).

**16. Potential Benefits to the Subject**

**Are there potential benefits to the subjects that may reasonably be expected from participation in the research?**

Yes

**Describe.**

Participants will receive treatment of destructive behavior and teaching of functional communication skills.

**17. Potential Benefits to Society**

**What are the anticipated benefits (i.e., value) to society that may reasonably be expected to result from this research?**

The results of the current investigation may extend the literature on the effectiveness of FCT for individuals with severe destructive behavior by identifying the generality of FCT effectiveness.

**18. Alternatives to Participation**

**Are there any reasonably available alternatives in the non-research context which would have the potential for providing the same benefits to subjects?**

Not applicable. There are no direct benefits to subjects; the alternative is to not participate in the research.

♦ Yes. Describe: The parents of potential participants will be informed that they are free to choose whether or not to participate in the current study. Participants will have the opportunity to receive services from the Munroe-Meyer Institute or from other facilities, regardless of their participation in this study. Parents of participants assigned to the waitlist control condition will be given a packet of information regarding local intervention services outside of Munroe-Meyer Institute's Center for Autism Spectrum Disorders.

No. Explain:

